## ***1.2. PATIENT FOLLOW-UP***

The objectives of post-treatment follow-up are to:

- detect local or remote recurrences,
- detect and manage late complications related to treatment as well as sequelae,
- organize the necessary supportive care,
- ensure the quality of life
- early detection of a second cancer.

The current monitoring framework includes a clinical examination and a biological assessment every 3 months for 2 years and then every 6 months up to 5 years and an imaging assessment every 6 months. However, the value of this systematic imaging surveillance is controversial (4-7) and no randomized study has been carried out on this subject. Several observational studies suggest that systematic imaging surveillance can detect patients with asymptomatic relapse, but none show earlier relapse detection (8, 9), nor any difference in survival.

According to Voss et al for patients (children or adolescents) followed for Hodgkin lymphoma in remission, the majority of relapses were detected by the appearance of symptoms, clinical manifestations or laboratory abnormalities (4, 10-13).

Another problem is the repeated exposure to radiation during each scan with a potentially increased risk of a second cancer (15, 16). These imaging tests can also generate anxiety in patients in asymptomatic remission, especially just before and while awaiting the results of these tests. Imaging

CONFIDENTIAL

assessment can lead to the detection of false positives, which involves performing additional examinations, including biopsies that are also painful, expensive and anxiety-inducing (14).

These constraints would be acceptable if the relapse was detected before clinical manifestations and allowed patient survival to be increased.

Thompson et al recently published the results of a study regarding the utility of imaging surveillance in a large cohort study in patients with diffuse large B-cell lymphoma. Routine imaging surveillance allows detection of asymptomatic relapse in only 1.7% of patients (17, 18).

In this context, Huntington et al assessed the medico-economic impact of routine imaging surveillance. The results show that the clinical benefit of systematic imaging monitoring of asymptomatic patients in remission is very low or even zero compared to the substantial cost incurred (19).

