### **1.3. MOOVECARE TOOL FOR LYMPHOMA RELAPSE DETECTION**

We have developed a score based on the dynamics and the combination of clinical and biological signs to alert the doctor of a possible recurrence of lymphoma

[figure not shown]
The considered clinical symptoms will be self-assessed (presence / absence or no problem / slight problem / medium problem / significant problem) by patients every 1 to 2 weeks, sent by their Smartphone or computer via the Internet, and will be analyzed by software that determines whether or not a relapse or significant complication is likely. The referring doctor will thus be alerted early and will summon the patient early for a check-up.

A similar application has been developed to detect relapse of lung cancer early (20, 21). The prospective study of this application showed interesting results in these patients with 100% sensitivity, 89% specificity, 81% PPV and 100% NPV with 11 symptoms studied. In the initial study to establish a detection algorithm based on only 6 symptoms, a NPV of 93% was already noted (20). In addition, relapses were detected on average 5 weeks before the scheduled date of the follow-up assessment (images every 3 months) (21).

An analysis of overall survival (monocentric and non-randomized) in our center also suggests a gain in survival of nearly 24% at 1 year ( $p = 0.02$ ) (22). This gain in survival is most likely related to the early initiation of salvage treatment and supportive care.

In the follow-up of the patients, it appeared that the algorithm was more sensitive if the patients were not very symptomatic at inclusion and had an initial score of less than 7 (by adding the scores of 0 to 3 for the symptoms concerning cough, dyspnea, pain, anorexia and asthenia: no problem = 0, mild problem = 1, medium problem = 2, significant problem = 3). A phase 3 study comparing this computerized surveillance with surveillance according to the usual method is in progress.

The results of the interim study suggest a favorable trend in overall survival in user and compliant patients (use at least once a week): 62% in the standard arm versus 87% in the SENTINEL arm:  $p(\text{logrank})=0,038$  (23).

Results of the interim analysis of the phase 3 study  
Per-protocol analysis of overall survival ( $p=0,038$ ).

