## **2.2. SECONDARY OBJECTIVES AND ENDPOINTS**

### **2.2.1. Secondary objectives**

The interest of web-application monitoring will also be assessed in terms of:

- progression-free survival,
- overall patient survival at 2 years,
- estimated time between the diagnosis of a complication, allowed by the application, and the theoretical date of the scheduled subsequent follow-up,
- proportion of hospitalization for life-threatening emergencies,
- total number of complications observed,
- quality of life of patients,
- the degree of patient compliance with the use of the web application
- the degree of satisfaction with the use of the web-application and the implementation of web-monitoring,
- number of significant complications whatever they may be (but defined above), which have arisen and not identified via the application (sensitivity calculation),
- number of significant complications whatever they may be (but defined above), which have arisen and identified in the systematic follow-up group, excluding systematic follow-up,
- Performance Status at relapse,
- description of health consumption in the 2 groups.

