### **2.2.2. Secondary endpoints**

Progression-free survival is defined as the time between the date of the first examination making the diagnosis of partial response or complete response and the date of consultation allowing the diagnosis of the relapse.

The diagnosis of partial or complete response, as well as relapse in this study follows the definition of the Cheson criteria.

The time between the date of diagnosis of the relapse and the nearest consultation date scheduled as part of the standard follow-up will be evaluated. The same will be done with the date of diagnosis of significant complications.

The time taken to set up a treatment will also be evaluated. Thus, the time between the date of diagnosis of each event and the date of implementation of the care (1st psychological consultation, date of D1 of treatment, etc.) will be evaluated.

Overall survival is defined as the time between the date of diagnosis of the complete or partial response as defined in chapter 2.1.2 and death from any cause within 2 years.

Quality of life will be studied using the QLQ-C30 and HUMEUR PhQ9 questionnaires at inclusion and then follow-up consultations at 3, 6, 9 and 12 months.

Patient compliance with the use of the web application will be assessed based on the number of assessments completed by patients; an evaluation every 14 days is expected. Patients who have completed less than 1 assessment per 42 days (6 weeks) will be considered non-compliant. An overall compliance rate over the entire period and a rate per 14-day period can then be presented.

The satisfaction and feelings of patients with regard to the web-monitoring and the use of the web-application will be assessed by a self-questionnaire during the follow-up visit in the 6th month.

The calculation of the application's sensitivity is based on the evaluation of the number of alerts triggered by the application against the results of systematic or alert-triggered imaging examinations.

CONFIDENTIAL

The Performance Status will be assessed according to WHO recommendations.

The description of health consumption will be assessed by the number of consultations, imaging and laboratory tests performed by the patients in each group.

[figure not shown]

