## **5.2. *STUDY EVALUATIONS***

The type of follow-up the patient will benefit from will be assigned by randomization.

Patients will be able to benefit from the supportive care adapted to their situations. The need for this supportive care can be detected during consultations or through the application.

All patients will be seen in consultation every 3 months with a clinical examination including estimation of the PS and a biological assessment (according to the clinician's habits).

The questionnaires (QLQ-C30 and PhQ-9) will be completed again at the 3,6-,9- and 12-month follow-ups.

For patients randomized to the "standard" arm, a systematic imaging workup (minimum TAP CT (cervical at best)) will be performed every 6 months corresponding to standard follow-up.

Patients randomized to the "Web-application follow-up" arm will perform a self-assessment of symptoms via the Moovcare application with a maximum interval of 14 days between 2 seizures, and if necessary, each time symptoms appear.

In the event of a Moovcare alert (and telephone call to the patient) suggesting a relapse or a complication, a CT scan and / or other evaluation examination (PET, biopsies, etc.) will be scheduled within ideally less than 14 days depending on the type of alert.

CONFIDENTIAL

To be able to connect to the application, included patients will receive personal access codes to the application by email with instructions for use:

- access to the application is via a username and password,
- the password is encrypted in the host's database,
- access to the application is via a secure SSL connection (https) which is a protocol for securing data exchanges between the client and the application server,
- a brute force intrusion detection system makes it possible, when too many connection attempts are detected, to deactivate the account in question.

A satisfaction questionnaire will be taken at the 6-month follow-up.

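### The lead-time objective runs to the next scheduled follow-up, but the endpoint runs to the nearest scheduled consultation, which may already be past

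*Combined protocol and SAP*

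**What the plan says.** Section 2.2.1 lists, as one of its secondary objectives, the "estimated time between the diagnosis of a complication, allowed by the application, and the theoretical date of the scheduled subsequent follow-up". That reference date looks forward only.

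Section 2.2.2 defines the corresponding measure for relapse as "The time between the date of diagnosis of the relapse and the nearest consultation date scheduled as part of the standard follow-up". It then adds: "The same will be done with the date of diagnosis of significant complications". For complications, one quantity therefore has two reference dates. For relapse, section 2.2.1 has no separate lead-time objective, so section 2.2.2 is the only definition.

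Neither section gives a sign convention, limits *nearest* to visits still to come, or says whether the inclusion visit counts as a reference. The description of planned statistical methods in section 6.2 covers this endpoint only through a general mention of event times, which does not settle the matter.

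The visit calendar is clear. Section 5.2 states: "All patients will be seen in consultation every 3 months". The tables in section 5.3 show M3 to M24 in both arms. Section 1.2 gives the same spacing for standard follow-up.

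**The concern.** Earlier diagnosis is the rationale for the tool, and this endpoint measures it directly, in weeks. Section 1.3 motivates it with a forward measure from the lung cancer application, where "relapses were detected on average 5 weeks before the scheduled date of the follow-up assessment".

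A nearest-visit rule does not measure that. A diagnosis made soon after a visit is the one with the most time saved before the next visit, and it is also the one whose nearest visit is the past one. It receives a small value, or a negative one if a sign is kept. An analyst programming from section 2.2.2 would take the minimum distance and report a number that does not answer the objective in section 2.2.1.

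**Working it through.** **Inputs.** The visit interval is 3 months (sections 5.2 and 5.3): L = 3 × 365.25 / 12 / 7 = 13.04 weeks, so L/2 = 6.52 weeks. The timing of unscheduled diagnoses within an interval is not given and has to be assumed. The plan states no expected lead, precision or power for this endpoint, so there is no figure to reproduce.

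**Step 1: one diagnosis.** Let t be the weeks since the last visit.

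- Lead to the next visit: L − t.
- Distance to the nearest visit: min(t, L − t). The past visit is used whenever t < L/2.
- At t = 3: next = 13.04 − 3 = 10.04 weeks; nearest = 3 weeks, or −3 if signed.
- At t = 10: both rules give 13.04 − 10 = 3.04 weeks.

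The rules agree in the second half of the interval. In the first half, the unsigned value falls short of the forward lead by L − 2t, which grows as the diagnosis comes earlier.

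**Step 2: even timing between two eligible visits (assumption).**

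- Mean to next: L/2 = 6.52 weeks, range 0 to 13.04.
- Mean absolute distance to nearest: L/4 = 3.26 weeks, maximum 6.52.
- Mean signed distance to nearest: 0.
- Share timed against a past visit: 50%.

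A simulation of 400,000 diagnosis times gave the same values to within 0.01 week, with a share of 50%. With L rounded to 13 weeks the means are 6.5 and 3.25.

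**Step 3: skewed timing.** Let U = t/L. The share timed against a past visit is P(U < 0.5), which is 0.5^a for Beta(a,1) and 1 − 0.5^b for Beta(1,b). The means are from simulation.

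| Timing of U | Past visit used | Mean to next (weeks) | Mean absolute to nearest (weeks) |
|---|---|---|---|
| Beta(3,1), late | 12.5% | 3.26 | 2.85 |
| Beta(2,1) | 25% | 4.35 | 3.25 |
| Even | 50% | 6.52 | 3.26 |
| Beta(1,2) | 75% | 8.69 | 3.26 |
| Beta(1,3), early | 87.5% | 9.79 | 2.85 |

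The forward lead triples from the first row to the last (3.26 to 9.79), while the unsigned nearest-visit mean is 2.85 in both. Without a sign, the measure as written cannot tell late detection in the interval from early detection.

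**Step 4: inclusion visit not a reference.** A diagnosis before M3 then has M3 as its nearest visit, and its lead can reach 13.04 weeks. Under even timing over H months, the share timed against a past visit is 0.5 × (1 − 3/H):

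- H = 6: 0.5 × 0.5 = 25%.
- H = 12: 0.5 × 0.75 = 37.5%.
- H = 24: 0.5 × 0.875 = 43.75%.

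The simulated mean absolute distances are 4.90, 4.08 and 3.66 weeks, against about 6.5 to the next visit in each case.

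**The case against.** The strongest reply is that this is loose wording and not a chosen rule. The English text is visibly a translation, section 2.2.1 supplies the forward meaning, and section 1.3 uses the same forward concept. Read alongside its own objective, *nearest* may mean nearest upcoming. That is possible and cannot be excluded. It makes the correction easier but does not remove the need for it, because section 2.2.2 is the operative definition and nothing in it restricts the direction.

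The second reply concerns weight. This is one of twelve secondary objectives, with no hypothesis or decision rule. Whether events are identified early is already addressed by the primary comparison in sections 2.1.2 and 6.2. This stands: the trial does not lose its means of showing earlier identification, and only the measure in weeks is affected. Comparison with the 5-week lung figure is not a planned analysis either, and that figure came from a schedule of imaging every 3 months.

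A reader might also infer from the objective's restriction to diagnoses made through the application that the endpoint has no standard-arm value. The documents do not support that. The restriction is in section 2.2.1, whereas the definition in section 2.2.2 names no arm. What is missing is an explicit statement that the value will be shown by arm.

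**Conclusion.** The contradiction holds. For complications, sections 2.2.1 and 2.2.2 give different reference dates for the same interval. Taken literally, the second shortens or reverses the largest leads and does not measure the stated objective. This follows from the 3-month calendar and the wording alone.

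The sizes rest on an assumption about timing that the documents do not supply. Even timing between two eligible visits gives 6.5 weeks to the next visit, against 3.25 (absolute) or about 0 (signed) to the nearest.

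Two stronger statements are tempting. A reader might infer that half of unscheduled diagnoses would be timed against a past visit. That needs even or symmetric timing with inclusion as a reference visit; the share was 12.5% to 87.5% under the skewed timings tried, and 25% (6 months) to 44% (24 months) under even timing without inclusion as a reference. A reader might also infer that no lead can exceed 6.5 weeks. That ceiling holds only between two eligible visits and fails before M3 if inclusion does not count.

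This is a point to correct in a secondary endpoint.

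**What to change.** In section 2.2.2, replace the nearest consultation date with the next scheduled consultation date after the diagnosis, taken from the theoretical M3–M24 calendar in section 5.3. State that a positive value means diagnosis before that visit, and give 0 to events diagnosed at a scheduled visit. Apply the rule to relapses and to significant complications, and tabulate it by arm, with the number of zero values shown beside the mean so that the share of off-schedule diagnoses is visible.

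Present the table as descriptive. A difference between arms should not be called the lead time caused by the application: it is conditional on having an event, which is a subset formed after randomisation, and part of any value reflects visit spacing. Off-schedule diagnoses spread evenly over the interval average 6.5 weeks before the next visit whether or not the application brought them forward.

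The cost is a wording change and one table. Diagnosis dates are already needed for other endpoints in section 2.2.2. The e-CRF is not among the documents, so it should be checked that these dates are recorded for complications in both arms.

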#### **2.1.2. Primary endpoint**

The primary endpoint is the appearance of a significant complication detected and confirmed by a medical consultation performed outside of standard follow-up.

The significant complications are:

- emergency hospitalization,
- a medical consultation without follow-up with medical prescription (imaging / drug prescription)
- a significant event at the classic follow-up consultation (very degraded PS, antibiotic therapy, supportive care with consultation, pulmonary embolism, sepsis, severe depression, etc.)

We will identify in the web-app group, the absence of alert in the event of complications and in the standard arm, the absence of medical consultation (attending physician) in the event of complications.

Complications diagnosed during the follow-up consultation will be reviewed in the form of a list by the coordinator, who will rule on the significance of the complication.

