### 5.3. SCHEDULE OF THE STUDY

*For patients randomized to the “standard” arm:*

	Baseline	M3	M6	M9	M12	M15	M18	M21	M24
Eligibility criteria	X								
Study presentation / Written inform consent	X								
Cancer history	X								
Physical exam (PS, weight)	X (- 15 days)	X	X	X	X	X	X	X	X
Biology report (parameters at the discretion of the investigator)		X	X	X	X	X	X	X	X
Initial Symptom score	x								
Imaging assessment	X (- 4 weeks)		X		X		X		X
Quality of life questionnaires	X	X	X	X	X				

*For patients randomized to the “web-application follow up” arm:*

	Inclusion	M3	M6	M9	M12	M15	M18	M21	M24
Eligibility criteria	X								
Study presentation / Written inform consent	X								
Cancer history	X								
Physical exam (PS, weight)	X (- 15 days)	X	X	X	X	X	X	X	X
Biology report (parameters at the discretion of the investigator)		X	X	X	X	X	X	X	X
Initial Symptom score	x								
Self assessment	Every 14 days maximum for patients included in the “web application follow-up” arm								
Imaging assessment	X (- 4 weeks)	In the event of a Moovcare alert or clinical call point							
Satisfaction questionnaire			X						
Quality of life questionnaires	X	X	X	X	X				

CONFIDENTIAL

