## **6.2. STATISTICS**

### **6.2.1. Description of planned statistical methods**

This study should allow us to evaluate the functioning of the application in a follow-up context in patients with lymphoma at high risk of relapse.

The patient sample for this analysis will consist of all patients, included in the study and meeting all the eligibility criteria described in Chapter 4, who have signed a consent.

The initial characteristics of the analysis population (demographic data, disease, previous and concomitant treatments, prognostic factors, etc.) and all the evaluation criteria described in paragraph 2 will be presented globally

For the qualitative variables, we will present the number as well as the percentage. For quantitative variables, we will present the median or the mean plus or minus the standard deviation depending on the normality of the variable, the minimums and maximums will also be indicated.

Events, as defined in chapter 2.1.2. (apart from relapse) will be described in terms of frequency by etiological type (HLT or HLG T according to the MedDRA classification) and by severity according to NCI CTCAE v4.02.

For the analysis of the censored data (overall survival and other timeframes of events), the survival curves will be plotted according to the Kaplan-Meier estimates, the medians of survival will be presented as well as their 95% confidence intervals.

For performing multivariate survival analyzes, the semi-parametric Cox model will be used to calculate the odds ratios which will be presented with their 95% confidence interval.

The sensitivity of the application to detect a relapse and / or significant complications will be calculated.

Quality of life scores will be calculated according to EORTC guidelines for the QLQ-C30. The quality of life will be described at each measurement time and compared to inclusion and then studied longitudinally using mixed analysis of variance models for repeated measures.

PHQ9 scores will be calculated according to the recommendations, described at each measurement time and compared to inclusion. The classes proposed in the literature ( $\leq 4$ ; 5-14;  $> 14$ ) will be used to describe the state of depression of patients.

The analyzes will be carried out with SAS 9.3 software (SAS Institute Inc. Cary, NC, USA).

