### **6.2.1. Sample size determination**

The main objective of the study is to show that follow-up via the SENTINEL Lymphoma web-application could make it possible to better identify the significant complications occurring between two systematic follow-up consultations with the specialist in patients followed for high-risk lymphoma. relapse than with standard follow-up. The evaluation of the main objective will be carried out over 6 months of follow-up.

This study is based on a pooled triangle test analysis (24, 25, 26). Two groups will be composed, one will be monitored via the web-application, the other will be monitored in a standard way (consultation and imaging).

A 1: 1 randomization will assign the treatment group to the patient. Stratification on center, autologous transplant, PS, relapse and lymphoma type will be performed to ensure the comparability of our two populations at inclusion.

This sequential method will make it possible to evaluate during recruitment the diagnostic efficiency of significant complications outside systematic consultations while controlling the power (risk of accepting our null hypothesis wrongly) and the type I error (risk of rejecting our wrongly null hypothesis). This design allows us to consider stopping the trial as soon as the information gathered is sufficient to conclude. We will be able to conclude that the web-application is diagnostic efficiently or, on the contrary, that it is lacking in interest.

We set the risk of the first species alpha at 5%, the potency at 90%, we envisage that monitoring via the web-application allows us to identify significant complications between two systematic follow-ups in 90% of patients (i.e. 10% of patient presenting an event not identified early) against 60% (i.e. 40% of patient presenting an event not identified early) in the group followed in a standard way (i.e. a difference of 30%).

The early unidentified event is defined:

- in the web application follow up group by the absence of an alert in the following cases:
  - emergency hospitalization,
  - a medical consultation without follow-up with medical prescription (imaging / drug prescription)
  - a significant event at the classic follow-up consultation (very degraded PS, antibiotic therapy, supportive care with consultation, pulmonary embolism, sepsis, severe depression, etc.)
  
- – in the standard group in the following cases:

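### Section 2.2.2 measures the app's sensitivity against imaging that web-arm patients without an alert are not scheduled to have, and is not reconciled with Sections 2.2.1 and 6.2.1

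*Combined protocol and SAP*

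**What the plan says.** Three places describe the sensitivity of the application.

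- Section 2.2.2 rests it on the "evaluation of the number of alerts triggered by the application against the results of systematic or alert-triggered imaging examinations". It gives no numerator or denominator.
- Section 2.2.1 lists, as a secondary objective, the number of significant complications "which have arisen and not identified via the application (sensitivity calculation").
- Section 6.2.1 (Description of planned statistical methods) states: "The sensitivity of the application to detect a relapse and / or significant complications will be calculated". It gives no formula and no reference standard.

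Imaging differs by arm. For the standard arm, Section 5.2 says that "a systematic imaging workup (minimum TAP CT (cervical at best)) will be performed every 6 months". For the web arm, the imaging row in Section 5.3 after baseline reads only "In the event of a Moovcare alert or clinical call point". Self-assessment through the app is done in the web arm alone.

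Separately, the primary endpoint does look for web-arm events that raised no alert. Section 2.1.2 says "We will identify in the web-app group, the absence of alert in the event of complications", and Section 6.2.1 (Sample size determination) defines an early unidentified event "in the web application follow up group by the absence of an alert in the following cases".

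**The concern.** Sensitivity is the share of true events that the tool flags, so it needs a reference result for events that were not flagged. The two kinds of imaging named in Section 2.2.2 do not supply one. Systematic scans belong to patients who cannot generate an alert, and alert-triggered scans belong by definition to patients who did. The rule cannot register a miss, yet misses are what Section 2.2.1 says the calculation is about.

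The risk is to reporting. An analyst could produce 100%, a positive predictive value or a genuine sensitivity, all under one label and chosen after the data are seen. A literal 100% could also stand in the same report as web-arm patients whom the primary analysis counts as having an event with no alert.

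**Working it through.** The plan states no expected sensitivity and no expected number of events, so there is no figure to reproduce. Event counts and imaging shares below are assumptions.

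**1. Who has a qualifying reference result after baseline (Sections 5.2 to 5.4)**

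| Group | Alert possible | Systematic imaging | Alert-triggered imaging |
|---|---|---|---|
| Standard arm | No | Every 6 months | No |
| Web arm, event with alert | Yes | None scheduled | Yes, if doubt persists after the call |
| Web arm, event without alert | Did not occur | None scheduled | No |

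The last row can be scanned only at a clinical call point, which Section 2.2.2 does not name.

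**2. Literal reading.** Sensitivity = TP/(TP + FN), where TP is events with an alert and FN is events without one. With no reference result for the last row, FN = 0. For 20 web-arm events (assumed):

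| True sensitivity | Section 2.2.2, literal | All events counted (Section 2.2.1) | Wilson 95% CI |
|---|---|---|---|
| 50% | 10/10 = 100% | 10/20 = 50% | 30–70% |
| 70% | 14/14 = 100% | 14/20 = 70% | 48–85% |
| 90% | 18/18 = 100% | 18/20 = 90% | 70–97% |

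**3. Alternative reading.** If alerts are the denominator and imaging-confirmed alerts the numerator, the result is TP/(TP + FP), where FP is alerts not confirmed. That is a positive predictive value and again contains no misses. The protocol's own precedent shows that the two measures differ: Section 1.3 reports 100% sensitivity but an 81% PPV for the lung cancer application.

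**4. Admitting call-point scans.** Let s be true sensitivity, and a and v the shares of alerted and non-alerted events that are imaged. Apparent sensitivity = s·a / [s·a + (1 − s)·v]. With s = 0.60:

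- a = 1, v = 0.25: 0.60/(0.60 + 0.10) = 86%
- a = 1, v = 0.5: 0.60/(0.60 + 0.20) = 75%
- a = 1, v = 1: 0.60/(0.60 + 0.40) = 60%
- a = 0.6, v = 0.8: 0.36/(0.36 + 0.32) = 53%

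The bias vanishes only at a = v and reverses when a < v. The documents give neither share.

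**5. Events that imaging does not establish.** Sepsis and severe depression are listed as significant complications in Section 2.1.2. An imaging reference cannot cover them under any reading.

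**6. Scale in the plan's own terms.** The planning value for the web arm is "10% of patient presenting an event not identified early", with the main objective evaluated over 6 months. At the maximum of 40 patients, 0.10 × 40 = 4 such patients. None would register under the literal rule. No sensitivity follows from this, because the total number of events is not given.

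**7. Why a corrected definition needs a time window.** Assume a 2% chance of an unrelated alert per fortnightly assessment. Over 26 assessments (12 months), 1 − 0.98^26 = 41% of patients would have had one. If any earlier alert counted as detection, a true 60% would appear as 0.60 + 0.40 × 0.41 = 76%.

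**The case against.** The strongest reply is that Section 2.2.2 is underspecified rather than wrong. The English is visibly a translation, the sentence gives no fraction, and Sections 2.2.1 and 2.2.2 might be meant as complementary: imaging for relapse, event counts for complications. The combined wording in Section 6.2.1 (Description of planned statistical methods) could fit that. This stands in part. It is why 100% is one reading only, and why the sections are better called unreconciled than flatly contradictory. It does not rescue the rule, since even for relapse alone an un-alerted web-arm patient has no qualifying scan.

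A second reply is that imaging is spaced out, not removed. Sections 1.5.1.2 and 1.5.3 speak of spacing, and the hypotheses in Section 6.2.1 (Sample size determination) mention systematic imaging without distinguishing arms. None of these gives a web-arm imaging interval, and Section 5.3 schedules none.

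A third reply is that missed events are already captured. For complications this is right, through the primary endpoint. A reader might infer from the point above that the trial does not collect misses, or that the primary comparison is compromised. The documents support neither. The fault lies in one secondary definition.

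**Conclusion.** The point holds, at the level of a change that should be made. Under the wording of Section 2.2.2, web-arm events without an alert cannot count as misses, so the result is either 100% by construction or a positive predictive value. Admitting call-point scans leaves a bias of unknown direction unless alerted and non-alerted events are imaged equally often. The conclusion rests on the schedule in Section 5.3.

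Two stronger inferences are not supported. The report will not necessarily show 100%, since the sentence fixes no fraction. Nor can the likely error be sized from the plan: the 10% figure is a 6-month planning value for patients, and should not be combined with the 20–40% relapse rate over 2 or 3 years in Section 1.1 to yield a sensitivity. The illustrations show the mechanism, not a forecast. The measure is secondary and descriptive, and the primary test and sample size are untouched.

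**What to change.** Replace the sensitivity sentence in Section 2.2.2 and align the one in Section 6.2.1 (Description of planned statistical methods). In the web arm, define sensitivity as events with an associated alert divided by all events found by any route, whether or not imaged. Report it separately for:

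- relapses by the Cheson criteria, taken from progression-free survival follow-up to 24 months (relapse is not in the Section 2.1.2 list, so the primary endpoint does not supply it);
- significant complications as defined in Section 2.1.2, over the 6-month primary period, using the existing coordinator review and the same alert/no-alert rule as the primary endpoint.

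Fix before analysis the unit (each event, or first event per patient), the observation period and one alert-to-event window, so that an earlier unrelated alert does not count as detection. The primary rule states no window; if the one chosen is not used there too, the report should explain why the two counts differ. Give exact 95% confidence intervals. Report the share of alerts confirmed on work-up separately, as positive predictive value.

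Cost: no added scans or visits. Alert dates held in the application must be linked to e-CRF events. Reported sensitivity may be lower. Precision will be low: if the general 20–40% relapse rate applied to 40 web-arm patients (an assumption, since this trial enrols high-risk patients), there would be 0.20 × 40 = 8 to 0.40 × 40 = 16 relapses, and exact 95% intervals of 24–91% for 5/8 and 35–85% for 10/16. Asymptomatic relapses never detected in the web arm stay uncounted and should be stated as a limitation.
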